3.3.4. STUDY DRUG HANDLING

Instructions for study drug receipt, handling, storage and administration are available in the manuals concerning study drug and IWRS.

Packaging and Labeling

The study drug will be labeled in accordance with Annex 13 of EudraLex Volume 4 requirements and local regulations. Each label will contain but will not be limited to, study number, storage conditions, dosing instructions, Sponsor's name, address and telephone number.

One kit consists of a box containing 2 syringes. A randomization system will assign each of the treatment kits to a subject. The content of each treatment kit will be determined according to the randomization schedule.

Storage

Study drug will be provided under refrigerated conditions and must be stored in a secure, limited-access location under the storage conditions specified by the Sponsor.

ALX-0061 and placebo must be refrigerated at 2°C to 8°C (35.6 °F to 46.4 °F) and should be stored in the secondary packaging (sealed box) until administration. It should not be frozen or shaken.

Site storage conditions should be monitored by the site personnel and reviewed by the monitor during site visits. Deviations from the storage requirements must be documented and reported to the Sponsor, according to the instructions provided in the manual concerning study drug.

Dispensing

The Investigator or qualified designee(s) will dispense study drug to subjects who have met the entry criteria. Clinical supplies may not be used for any purpose other than that which is stated in this protocol.

Product Quality Complaint

Any malfunctioning pre-filled syringe has to be communicated (written or electronically) and returned to the Sponsor or its designee upon Sponsor's request.

3.3.5. STUDY DRUG INJECTIONS

ALX-0061 s.c. or placebo s.c. injections, as applicable, will be administered using the single-use pre-filled syringe by an appropriate licensed and authorized health professional.

At each administration, the subject will receive two s.c. injections in succession at a different quadrant in the abdominal region. As injections are to be performed q2w, the injections can be performed in an abdominal quadrant of choice. However, note that the area of administration needs to be evaluable for local skin reaction (normal skin without skin burns, scars or large tattoos in the area of administration). The abdominal quadrants used for the administrations will be recorded in the (electronic) Case Report Forms ([e]CRFs). At least until Week 12, subjects will remain at the site for 60 minutes after the injection in order to assess adverse reactions.

In case of an injection site reaction, it has to be followed-up and documented in which exact quadrant the skin reaction appears.

Detailed instructions for study drug administration are available in the manual concerning study drug.

3.3.6. MEDICATIONS OTHER THAN STUDY DRUG

Previous and concomitant medication will be recorded in the Patient's Medical File and in the (e)CRF up to the Follow-up Visit.

An overview of corticosteroid handling throughout the study can be found in Appendix 9.5.

3.3.6.1. MEDICATIONS STARTED PRIOR TO FIRST DOSING

Standard of care therapy for SLE:

The dose of oral corticosteroids (equivalent to ≤ 25 mg of prednisone/day) should have been stable for at least 4 weeks prior to baseline.

If subject is on antimalarials, he or she must have received antimalarials for at least 12 weeks with a stable dose of max. 400 mg/day for at least 4 weeks prior to baseline.

If subject started immunosuppressants prior to first dosing and is still taking this medication at baseline: azathioprine (max. 150 mg/day), mycophenolate mofetil (max. 2.0 g/day), methotrexate (max. 25 mg/week), cyclosporine (max. 200 mg/day), leflunomide (max. 20 mg/day), treatment duration must be at least 12 weeks with a stable dose for at least 4 weeks prior to baseline; either alone or in combination with corticosteroids and/or hydroxychloroquine.

If subject is on ACE inhibitor or angiotensin receptor blocker, the dose should have been stable for 4 weeks prior to baseline.

If subject is on NSAIDs, including aspirin and selective cyclooxygenase 2 inhibitors and other analgesics for SLE-related symptoms, the subject should receive stable doses of the usual marketed doses approved in the country in which the study is being conducted. After Week 24, the dose may be adjusted based on Investigator's discretion.

Prior use of any of the following medications is prohibited:

- If prior medications include immunosuppressants (i.e., if immunosuppressants were taken prior to first dosing but were stopped prior to the baseline visit), the last dose should have been received more than 4 weeks prior to baseline; for leflunomide and

hydroxychloroquine, a leflunomide or hydroxychloroquine treatment-free period of at least 12 weeks should be respected (unless an adequate cholestyramine wash-out was done for leflunomide).

- Use of any investigational or biological drug starting 6 months or 5 half-lives (whichever is longer) prior to baseline.
- Use of non-biological investigational therapies starting 4 weeks or 5 half-lives of the concerned therapy (whichever is longer) prior to baseline.
- Use of i.v. immunoglobulins, cyclophosphamide or tacrolimus within 12 months prior to baseline.
- Use of i.v., i.a., i.m. or high dose (> 25 mg/day) oral corticosteroids during the 4 weeks prior to baseline.
- Use of prior therapy blocking the IL-6 pathway, such as but not limited to ALX-0061, sirukumab, tocilizumab, sarilumab, clazakizumab, olokizumab, or JAK inhibitors at any time.
- Any live, attenuated vaccine within 3 months before dosing with ALX-0061, during the study or within 6 months after dosing.

3.3.6.2. THERAPY STARTED AFTER FIRST DOSING

Standard of care therapy for SLE:

- The dose of oral corticosteroids (equivalent to ≤ 25 mg of prednisone/day) should be kept stable as much as possible through Week 24.
- As an exception, the protocol allows for both dose decrease (tapering) and dose increase with the following limits:
 - If necessary based on the Investigator's clinical judgment, initiation of a short period (maximum 1 week) increase of prednisone (up to a maximum dose of 15/20/25/30 mg/day depending on the baseline dose; see table below) is allowed until the Week 4 visit (i.e., Week 4 \pm 5 days) with a return to the baseline value by Week 12. This increase is not allowed if the disease activity improves.
 - In case lowering of the dose of prednisone is desired before the primary endpoint, tapering can be allowed up to Week 12 according to the specifications below:

	Baseline dose	Increase for max. 1 week during first 4 weeks	Tapering allowed between Baseline and Week 12
1	16 to 25 mg/day	Increase to a maximum of 30 mg/day	No dose decrease below 50% of baseline dose
2	11 to <16 mg/day	Increase to a maximum of 25 mg/day	No dose decrease below 75% of baseline dose
3	7.5 to <11 mg/day	Increase to a maximum of 20 mg/day	No dose decrease < 7.5 mg/day
4	<7.5 mg/day	Increase to a maximum of 15 mg/day	No tapering will be allowed

- Between Week 12 and Week 24, no increase nor decrease of the dose in prednisone is allowed.

- After Week 24, tapering of the dose of oral corticosteroids to a target of ≤ 7.5 mg/day by Week 40 is recommended, at a rate that can be decided by the Investigator as clinically indicated. While tapering the dose between Weeks 24 and 40, an increase to the dose preceding the last taper step will be allowed.
- Doses for concomitant antimalarials and/or immunosuppressants must be stable for the duration of the entire study. The dose may be reduced or the medication temporarily discontinued for abnormal laboratory values, side effects, concurrent illness, or the performance of a surgical procedure, but the dose change and reason should be clearly documented.
- NSAIDs, including aspirin and selective cyclooxygenase 2 inhibitors and other analgesics for SLE-related symptoms during the study should receive the usual marketed doses approved in the country in which the study is being conducted. Doses must remain stable but may be changed at the discretion of the Investigator after Week 24 or if the subject develops unacceptable side effects.

Change to Standard of care therapy for SLE

In case of worsening of disease or a flare, the Investigator will decide on the need for increase of dose of oral corticosteroids, use of i.v. or i.m. corticosteroids, start or increase of the dose of anti-malarial or immunosuppressant. Subjects needing such change to standard of care therapy for SLE will be considered as treatment failures and imputed as non-responders in the analysis of the primary endpoint. This does not apply to the transient increase in oral corticosteroid (prednisone) dose that is allowed within the protocol until the Week 4 visit (i.e., Week 4 \pm 5 days) of the study (see above).

Prohibited Medication

Concomitant use of any of the following medications is prohibited while the subject is receiving the study drug and will prompt discontinuation of study drug:

- any investigational or biological drug.
- any live, attenuated vaccine within 3 months before dosing with ALX-0061, during the study or within 6 months after dosing.
- i.v. immunoglobulins, cyclophosphamide or tacrolimus.
- therapy blocking the IL-6 pathway, such as but not limited to ALX-0061, sirukumab, tocilizumab, sarilumab, clazakizumab, olokizumab, or JAK inhibitors.

Medicinal products which are metabolized via CYP450 3A4

Since IL-6 blocking might influence cytochrome P450 (CYP450) expression, subjects taking medicinal products which are metabolized via CYP450 3A4 (please refer to Flockhart, 2007

and Endres et al., 2006) will be closely monitored and their treatment will be adapted if necessary. For example, subjects on vitamin K antagonists will be monitored by assessment of international normalized ratio (INR) (see [Schedule of Assessments](#)), for subjects on statins, the lipid levels will be evaluated (see [Schedule of Assessments](#)), for subjects on cyclosporine, drug monitoring according to site routine practice should be performed.

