f) In case of worsening of disease or a flare, the Investigator will decide on the need for increase of dose of oral corticosteroids, use of i.v. or i.m. corticosteroids, start or increase of the dose of anti-malarial or immunosuppressant, according to his/her local clinical practice. The Investigator can also decide on whether study drug can be continued or not. Subjects needing such change to standard of care therapy for SLE will be considered as treatment failures and imputed as non-responders in the analysis of the primary endpoint. This does not apply to the transient increase in oral corticosteroid dose that is allowed within the protocol until the Week 4 visit (Week 4 \pm 5 days; see above).

Study Duration:

The anticipated maximum study duration per subject is 58 weeks after randomization; subjects will be followed for efficacy through Week 48 and for safety through Week 58.

The end of study is defined as the time of the last visit of the last subject participating in the study.

- **Screening Period:**
Subjects will be screened to confirm their eligibility for participation in this study within 4 weeks prior to baseline.
- **Treatment and Assessment Period:**
Eligible subjects will receive treatment at Week 0/Day 1 and up to and including Week 46. Subjects will return for ambulatory visits every 2 weeks.
All post-baseline visits may occur at the indicated week \pm 5 days throughout the study.

- Final Visit/ Early Termination Visit:
 - Subjects should return for the assessment visit at Week 48, and for the Follow-Up Visit at Week 58 (12 weeks after the last study drug administration at Week 46).
 - Subjects who discontinue study drug but are not withdrawing consent for post-treatment follow-up, should return for an early termination visit within 3 weeks after the last study drug administration. Subjects should also return for a Follow-up Visit 12 weeks after last study drug administration.

For details on visit assessments, see the Schedule of Assessments.

Discontinuation criteria:

Study drug administration must be discontinued in case of:

- Withdrawal of consent.
- Serious hypersensitivity reaction.
- Abnormalities in laboratory test results:
 - ALT and/or AST elevations:
 - $> 3 - \leq 5 \times \text{ULN}$, confirmed by repeat testing on 2 consecutive visits
 - $> 5 \times \text{ULN}$ (CTCAE \geq grade 3)
 - absolute neutrophil count $< 1 \times 10^9/\text{L}$ (CTCAE \geq grade 3)

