 - platelet count $< 50 \times 10^3/\mu\text{L}$ (CTCAE \geq grade 3)
- Diagnosis or suspicion of a serious infection (requiring parenteral antibiotics and/or hospitalization) if interruption of study drug is needed for more than one dose or if deemed necessary by the Investigator.
- Diagnosis of TB.
- Malignancy.
- Pregnancy or pregnancy planned within study period.
- Initiation of prohibited medication, as discussed with Sponsor/Medical monitor.
- In case of interruption of study drug administration for 2 consecutive doses.
- The randomization code is broken prematurely by the Investigator or his/her staff.
- Demyelinating disease.
- CHF class III or IV as defined by the New York Heart Association, unstable angina pectoris, myocardial infarction, cerebrovascular accident, thromboembolic event.
- If the Investigator or the Sponsor's Medical Monitor deems it is in the subject's best interest, e.g., in case of renal or CNS flare.

Discontinuation of study drug must be considered for subjects who develop a severe study drug injection-site reaction or a severe hypersensitivity reaction.

The Investigator will assess if study drug administration can be continued or not in case of change to standard of care therapy for SLE (except for forbidden treatment e.g.,

cyclophosphamide or another biologic, when study drug administration will be discontinued).

Assessments:

The following assessments are performed at the time points defined in the [Schedule of Assessments](#):

Efficacy evaluation

Primary endpoint: The primary endpoint is the percentage of subjects who achieved a response at Week 24 according to the composite mBICLA (BILAG-based Combined Lupus Assessment) score. mBICLA responders are defined as subjects who meet all of the following criteria:

- (1) BILAG-2004 improvement: all A scores at baseline improved to B/C/D, and all B scores improved to C or D.
- (2) no worsening in disease activity: no new BILAG-2004 A scores and ≤ 1 new B score.
- (3) no worsening of total mSLEDAI-2K score from baseline.
- (4) no significant deterioration ($< 10\%$ worsening) in Physician global assessment (PGA).
- (5) no treatment failure (i.e., new or increased immunosuppressives or anti-malarials; or non-protocol allowed increased oral or parenteral corticosteroids; or premature discontinuation from study treatment).

A modified SLEDAI-2K index (mSLEDAI-2K) will be derived from the standard index by omitting 1 of the standard items (low complement).

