9.5. OVERVIEW OF CORTICOSTEROID HANDLING THROUGHOUT THE STUDY

1) Keep doses stable if possible until Week 24

2) Increase to an absolute maximum dose of 15/20/25/30 mg/day depending on entry dose (as shown in table below) for a maximum of 1 week during the first 4 weeks with return to Baseline dose by Week 12 (increase only allowed if activity does not improve compared to Baseline)

4) Week 12-24: no change in prednisone dose is permitted (whether increase or decrease).

3) limit tapering to **Week 12** (following the rule as shown in table below)

Primary endpoint: mBICLA response Week 24

5) After Week 24, tapering to a target of < 7.5mg/day by Week 40 is recommended but the rate of tapering will be at Investigator discretion.

	Baseline dose	If necessary, increase allowed for 1 week during first 4 weeks	If desired, tapering allowed between baseline and Week 12
1	16 to 25 mg/day	Increase to a maximum of 30 mg/day	No dose decrease below 50% of baseline dose
2	11 to < 16 mg/day	Increase to a maximum of 25 mg/day	No dose decrease below 75% of baseline dose
3	7.5 to < 11 mg/day	Increase to a maximum of 20 mg/day	No dose decrease < 7.5 mg/day
4	< 7.5 mg/day	Increase to a maximum of 15 mg/day	No tapering will be allowed

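### Can the 1-week cap and the Week 12 return date on the early prednisone increase make the same steroid record both a treatment failure and a protocol-allowed course?

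*Protocol*

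**What the plan says.** **Allowance.** The Synopsis (standard of care medication, item a) and section 3.3.6.2 allow "initiation of a short period (maximum 1 week) increase of prednisone" up to the Week 4 visit, with the ± 5 day window spelled out, "with a return to the baseline value by Week 12. This increase is not allowed if the disease activity improves".

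**Tables and overview.** The column heading in the Synopsis and in 3.3.6.2 is "Increase for max. 1 week during first 4 weeks". Appendix 9.5, item 2, says "for a maximum of 1 week during the first 4 weeks with return to Baseline dose by Week 12", and its table heading is "If necessary, increase allowed for 1 week during first 4 weeks". None of these carries the visit window.

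**Link to the endpoint.** mBICLA criterion (5), in the Synopsis and sections 3.4.3.6 and 3.6.5, counts "non-protocol allowed increased oral or parenteral corticosteroids" as treatment failure. Section 3.6.5.1 imputes non-response for such subjects.

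**Exemption.** Where standard of care is changed for worsening or flare, the Synopsis (item f) and section 3.2.3.2 add: "This does not apply to the transient increase in oral corticosteroid dose that is allowed within the protocol until the Week 4 visit". Section 3.3.6.2 says the same: "This does not apply to the transient increase in oral corticosteroid (prednisone) dose that is allowed within the protocol until the Week 4 visit". The Synopsis and 3.3.6.2 versions also refer the reader back to the allowance set out earlier.

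**The concern.** Two features look wrong on first reading.

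First, one sentence caps the increase at 1 week and then sets a return date many weeks later. No passage says what status a dose has if it is still above baseline after the week has passed. Suppose a subject is raised on day 20 and is still above baseline on day 50. That subject meets the Week 12 deadline but exceeds the 1-week cap if the cap covers all time above baseline. The same record could then be coded as allowed or as failure.

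Second, the start limit is tied to a visit with a window in the text, but to the first 4 weeks in the headings and the appendix. A 7-day course begun on day 31, at a late Week 4 visit, satisfies the text and falls outside the heading.

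At stake is the steroid component of the primary endpoint. A failure call overrides every other mBICLA component. Sites also act on this rule when they prescribe, so a later coding rule cannot make uniform any courses that were given differently.

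**Working it through.** The plan gives no figure to reproduce here. The check is day arithmetic and a comparison of passages. Days are counted after baseline (day 0), so Week 4 = day 28 and Week 12 = day 84.

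**1. Time limits in the operative text (Synopsis item a; 3.3.6.2).**
- Week 4 visit window: 28 − 5 = day 23 to 28 + 5 = day 33.
- Latest end of a 1-week course: 33 + 7 = day 40. Earliest end, if started on day 0: day 7.
- Interval to the Week 12 deadline: 84 − 40 = 44 days to 84 − 7 = 77 days.

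**2. Do the two limits conflict?** If the week covered all time above baseline, every permitted course would be over by day 40, and a day-84 return date would do nothing. If the week caps the raise and the return date governs coming back to baseline, both clauses have effect. The 44 to 77 days are therefore not without a rule: the rule is return by Week 12, and Appendix 9.5 repeats it.

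The tapering column does not disturb this. Its floors lie at or below the baseline dose. In the lowest baseline row it rules out tapering altogether, while the next cell permits an increase. Read as covering descent from a raised dose, that cell would forbid the return which the text requires. The column must therefore concern going below baseline.

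**3. Does the failure definition catch the step-down?** Criterion (5) and section 3.6.5.1 both turn on an increase that the protocol does not permit. A dose falling from a permitted increase is not a further increase. The exemption in the Synopsis and 3.3.6.2 points back to the allowance as a whole, which includes the Week 12 return.

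**4. Start limit.**

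| Source | Limit | Latest day |
|---|---|---|
| Synopsis items a and f; 3.2.3.2; 3.3.6.2 (allowance and change-of-therapy paragraph) | Week 4 visit ± 5 days | 33 |
| Table headings (Synopsis, 3.3.6.2, Appendix 9.5); Appendix 9.5 item 2 | first 4 weeks | 28 |

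Difference: 33 − 28 = 5 days at most. A stricter reading, with the whole week inside the first 4 weeks, gives a last start on 28 − 7 = day 21, which is 33 − 21 = 12 days earlier. That reading conflicts with the text in the same section, which lets the increase be initiated up to the Week 4 visit.

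**5. Scale.** One subject in an arm of 60 is 1/60 = 1.67 percentage points. The documents give no frequency of such records. As an illustration only, take the protocol's 25% and 50% response rates, 60 per arm and a simple two-sided pairwise test at 5%. This is not the planned MCP-Mod analysis. If 2%, 5% or 10% of would-be responders in every arm were recoded as failures, power would go from 81.6% to 80.3%, 78.3% or 74.7%. These shares are assumptions and support no claim about the trial.

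**The case for a change.** The strongest case for a change is that this goes beyond missing SAP detail. The endpoint uses the protocol itself as the test of what is allowed, so the protocol's own limits must be unambiguous. Section 3.3.6 sends readers to Appendix 9.5 for the overview, and the appendix lacks the visit window. Version 3.0 clarified the Week 4 wording in the text but left the tables and appendix as they were. A SAP rule can settle the coding but cannot change courses already given.

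Part of this stands. The protocol never says outright whether time above baseline after the week is allowed, and the headings do not match the text. It does not follow that the endpoint is at risk. Failure is at most one possible reading, and the text does not force it. No passage shows that sites gave different courses. Deriving the steroid-failure flag is ordinary SAP content. Section 3.6.2 has the SAP finalized before database lock, 3.6.1 has deviations reviewed and classified before lock, and 3.6.5 gives the adjudication committee the task of judging whether data are suitable for the primary endpoint.

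The recoding could also fall unevenly across arms. With 10% of would-be responders recoded in one arm only, the 25-point difference becomes 0.50 × 0.90 − 0.25 = 20 points (active arm) or 0.50 − 0.25 × 0.90 = 27.5 points (placebo arm). Nothing in the documents suggests either pattern, and a flag derived before unblinding would be applied without knowledge of the arm.

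**Conclusion.** No change to the plan is needed. The wording is untidy: one sentence on the status of the step-down is missing, and the headings and overview differ from five agreeing statements by at most 5 days. An analyst following the text would derive the steroid-failure flag sensibly. Because the dose must be at baseline by Week 12 and may not change from then to Week 24, the ambiguity touches only the flag and not the steroid dose at the Week 24 assessment.

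The effect on the primary result is probably small but cannot be quantified, since the frequency of such records is not given. The 1.67 points per subject applies only to someone who meets every other mBICLA component and has exactly this kind of record. The conclusion assumes that the flag is defined once, before unblinding, and applied alike to all arms. It takes no position on the clinical limits, which are for the sponsor to set.
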